Regular use of intranasal corticosteroid (such as intranasal Fluticasone propionate 400 μ g per pipette; $\frac{1}{2}$ pipette 1-2 x /day to both nostrils or intranasal corticosteroid spray 1 dose 1-2 x /day to both nostrils if patient is not able to use the drops) is started at least 2 months prior to study entry. Regular CRSwNP and asthma medication is used throughout the whole study.

Exclusion criteria:

- Age <18 years
- CRS-surgery < 6 months before 1st visit
- pregnancy/ breastfeeding. FRPs need to perform pregnancy test prior to the CT/CBCT scans. If subject is already on contraception prior to the study this should be continued.
- complication of CRS (f.ex. mucocoele, invasive fungal rhinosinusitis). Take sinus CT/CBCT scans, if needed!
- acute rhinosinusitis/respiratory infection
- severe disease related to airways/ immunology: cystic fibrosis, primary ciliary dyskinesia (PCD), sarcoidosis, immunosuppression, diagnosed Specific antibody deficiency (SAD), CVI, HIV, fungal rhinosinusitis; Young syndrome; Kartagener syndrome;
- other severe disease such as active cancer
- Received biologic therapy/systemic immunosuppressant/ASA desensitization therapy/experimental monoclonal antibody treatment to treat inflammatory or autoimmune disease within 2 months of study entry or 5 half-lives, whichever is longer. The patient is allowed to use ASA dose <100 mg/day due to cardiovascular reasons after ASA desensitization.
- current immunotherapy
- communication problems (f.ge. neurological/psychiatric disease, language skills)
- unlikely to comply
- ASA-challenge negative.
- History of hypersensitivity to mepolizumab or excipients in the formulation

Power calculation: The mean postoperative difference in the Sinonasal Outcome test (SNOT-22) was assumed to be at least 9 between the treatment arms. In a previous study the response within each subject group was normally distributed with standard deviation 17. If the true difference in the experimental and control means is 13, we will need to study 57 experimental subjects and 57 control subjects to be able to reject the null hypothesis that the population means of the experimental and control groups are equal with probability (power) 0.8. The Type I error probability associated with this test of this null hypothesis is 0.05. The total number recruited is 120 (estimated rate of discontinuation is 5%).

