| Visits, hospitalisations, exacerbations, sick leave, productivity | Previous year | | | | | | | |
| Allergy test = serum specific IgE test (pölyerittely) | x | | | | | | | |
| | x | | | | | | x | |
| ASA challenge test (to subjects without previous challenge-test-confirmed NERD dg) | | x | | | | | | |
| Treatment with IMP | | | x | x | x | x | | |
| Check side-effects | | x | x | x | x | x | x | x |
| ENT visit (+ lung examination) | x | x | x | x | x | x | x | x |
| Check CRS control | x | x | x | x | x | x | x | x |
| Pulmonologist visit | x | | | | | | x | |
| Check asthma control | x | x | x | x | x | x | x | x |
| Questionnaire-packet: SNOT-22, 15D, AQLQ, Asthma control | x | x | x | x | x | x | x | x |

| | | | | | | | | |
|---|---|----|---|---|---|---|---|-------------------|
| test, 2xNetherlands-Q | | | | | | | | |
| VAS symptoms | | x | | | | | | |
| Baseline characters questionnaire (esitietokaavake) | x | | | | | | | (x) if changed |
| Acoustic rhinometry (ARM) | x | xx | x | x | x | x | x | x |
| nNO | x | xx | | | | | x | |
| eNO | x | | | | | | x | |
| Olfaction Sniffin' sticks | x | | x | x | x | x | x | x |
| sinus CT scans | x | | | | | | | |
| Blood analysis for Biobank | x | | | - | - | - | | - |
| Blood samples (5 EDTA tubes) for metabolomics & genomics | x | xx | x | x | x | x | x | x |
| Urine samples for metabolomics | x | xx | x | x | x | x | x | x |
| Fecal sample for microbiome | x | | x | x | x | x | x | x |
| Nasal samples (microbiome, transcriptomics, histology) | x | xx | | | | | x | |
| Spirometry | x | | | | | | x | |
| PEF 1 week | x | x | | | | | x | |
| microspirometry | | x | | | | | | |
| PEF at visit | x | x | x | x | x | x | x | x |
| PNIF at visit | x | x | x | x | x | x | x | x |
| Check disease relapse | x | x | x | x | x | x | x | x |
| Consider additional therapy /referral to operation | x | x | x | x | x | x | x | x |

Study endpoints

Primary, Change from baseline

endoscopic nasal polyp score (total score ranges between 0-8 of both sides), SNOT22 symptom score, VAS score (of smell loss, obstruction, postnasal drip, nasal discharge, facial pain/pressure) and, exacerbation-rate. Exacerbation means that patient has at least one of the following due to airway symptoms: oral corticosteroid course; antibiotic courses; sinus lavation; hospitalization.

Secondary, Change from baseline

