The statistical analyses will be conducted in the modified intention-to-treat (mITT) population, defined as all randomized participants who received at least one dose of the investigational medicinal product and fulfilled the inclusion criteria. One randomized participant was excluded due to failure to meet inclusion criteria, resulting in 47 participants per treatment group. All analyses were performed blinded to treatment allocation, and the randomization code was opened only after the trial was closed and the primary analyses completed. The sample size was calculated to provide 80% power to detect clinically meaningful differences in the coprimary endpoints using a two-sided significance level of 0.05. Baseline was defined as the recruitment visit, occurring approximately eight weeks prior to initiation of the investigational medicinal product. Participants received four injections over a 16-week treatment period, followed by an additional eight-week observation period without treatment, after which final measurements were obtained. Continuous variables are summarized using means with standard deviations or medians with interquartile ranges, as appropriate, and categorical variables using frequencies and percentages. The coprimary endpoints and all secondary continuous outcomes were analyzed as changes from baseline using linear mixed-effects models. These models included fixed effects for treatment group, time, and their interaction, and a random intercept for participants to account for within-subject correlation over repeated measurements. Group-specific changes from baseline were estimated at each follow-up time point, and treatment effects were assessed by comparing differences in these estimated changes between groups. Results are reported as mean differences with 95% confidence intervals. A two-sided significance level of $p < 0.05$ was applied to all analyses, and no formal adjustment for multiple comparisons was performed. Model assumptions were evaluated by visual inspection of residual plots to assess normality and homoscedasticity, and by examination of fitted values and influence diagnostics to identify outliers or model instability. The linear mixed-effects modeling framework was selected because it accommodates unequally spaced measurements and missing observations and provides unbiased estimates under the missing-at-random assumption.

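### A random intercept alone gives all visits one variance and one correlation, so late-visit confidence intervals can be too narrow if correlation fades or variance grows

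*SAP*

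**What the plan says.** The SAP's statistical analysis text covers the coprimary and the secondary continuous outcomes with one model: "The coprimary endpoints and all secondary continuous outcomes were analyzed as changes from baseline using linear mixed-effects models". The fixed effects are group, time and their interaction. Dependence within a participant enters through "a random intercept for participants to account for within-subject correlation over repeated measurements". No residual correlation structure, visit-specific variance, random slope or robust standard error is named. Treatment effects are the between-group differences in estimated change at the separate follow-up visits, with 47 participants per arm. On error control the SAP states: "A two-sided significance level of $p < 0.05$ was applied to all analyses, and no formal adjustment for multiple comparisons was performed".

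Model checking is by residual plots (normality, homoscedasticity), fitted values and influence diagnostics. No fallback model is given. The sensitivity analyses keep the same statistical models.

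Protocol Table 1 schedules SNOT-22 at all eight visits. Some outcomes are scheduled only at visits 1 and 7: eNO and spirometry in Table 1 ("Spirometry | x | | | | | | x"), and the blood count in Table 2.

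**The concern.** With a random intercept as the only dependence term, every visit has the same variance and every pair of visits the same correlation, whether 4 weeks or 28 weeks apart. The SAP justifies the framework partly by its handling of unequal spacing, but this covariance ignores spacing.

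Each visit's interval is then built from an average over visits. If correlation with baseline fades, the true variance of the change is below that average early and above it late. The error is misallocated across visits: early tests become conservative and late tests liberal. With p < 0.05 applied to every test and no multiplicity adjustment, nothing absorbs an excess at a late visit. Residual plots can show growing variance but not a wrong correlation pattern. Sensitivity analyses with the same model would share the fault, so their agreement would not reveal it.

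A narrower point concerns outcomes with one post-baseline value. If the response is a change score, each participant contributes one number, and a random intercept cannot be separated from residual error.

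**Working it through.** **Inputs from the documents.** 47 per arm; two-sided 5%; baseline about week −8 (SAP). Visits at weeks 0, 4, 8, 12, 16 and 20 (protocol Tables 1 and 2). The SAP's eight weeks after a 16-week period can be read as a last visit at week 24, so that was also run.

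**Assumed, because the documents do not give it.** The between-visit correlations and SDs. The protocol's power text has a single SD of 17 and compares two means. It reproduces (difference 9, SD 17, 80% power: 57 per arm) but says nothing about covariance over time.

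**Formulas.** Let V be the true covariance over T visits, and c_j = V_jj + V_00 − 2V_0j the true variance of the change at visit j.
- Reading A (response is the change score): the model uses the mean of the c_j at every visit.
- Reading B (baseline is a repeated response): the model uses 2 × (mean variance − mean off-diagonal covariance).
- R = c_j ÷ model variance; actual type I error ≈ 2 × [1 − Φ(1.96/√R)].

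**The plan's own figure.** With constant variance and correlation, R = 1 at every visit and the error is 5% under both readings. The nominal level is reproduced in that case.

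**Worked example.** Correlation 0.4 + 0.6 × 0.8^k, where k is the lag in 4-week steps, SD 1 at each visit. Then c_j = 1.2 × (1 − 0.8^k) for k = 2 to 7: 0.432, 0.586, 0.708, 0.807, 0.885, 0.948.
- Reading A: mean 0.728. Week 20: R = 0.948/0.728 = 1.303, √R = 1.142, 1.96/1.142 = 1.717, error 8.6%. Week 0: R = 0.432/0.728 = 0.594, error 1.1%.
- Reading B: mean correlation over the 21 visit pairs is 0.7315, so the model variance is 2 × (1 − 0.7315) = 0.537. Week 20: R = 0.948/0.537 = 1.766, error 14.0%. Week 0: R = 0.432/0.537 = 0.805, error 2.9%.
- In SNOT-22 points, if 17 is taken as the SD at each visit, SE = 17 × √(2 × variance/47). The week-20 SE should be 3.42; the model gives 2.99 (A) or 2.57 (B).

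**Other assumed patterns, to week 20. Type I error (%) at weeks 0 / 16 / 20:**

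| Pattern | Reading A | Reading B |
|---|---|---|
| Constant correlation 0.5, constant SD | 5 / 5 / 5 | 5 / 5 / 5 |
| 0.4 + 0.6 × 0.6^k | 2.3 / 6.3 / 6.6 | 4.0 / 9.3 / 9.6 |
| 0.4 + 0.6 × 0.8^k | 1.1 / 7.6 / 8.6 | 2.9 / 12.7 / 14.0 |
| 0.9^k | 0.6 / 8.3 / 10.0 | 2.3 / 14.7 / 17.0 |
| Correlation 0.5, SD rising linearly 1 to 1.5 | 2.9 / 6.4 / 7.5 | 1.8 / 4.5 / 5.5 |
| Correlation 0.4, baseline SD 1, later SD 1.5 | 5 / 5 / 5 | 3 / 3 / 3 |

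**Effect of the visit set** (the three fading patterns, week 20). Without week 0: A 5.9–8.5%, B 9.7–16.8%. Weeks 16 and 20 only: A 5.1–5.6%, B 8.0–10.2%. Over the wider set simulated with a last visit at week 20 or 24 (faster or slower fading, random slopes, growing SD), and leaving aside the constant-covariance and smaller-baseline-SD cases, the last visit ran at about 6–15% (A) and 5–19% (B).

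**After the fix.** With complete data, an unstructured covariance equals a t-test on change at each visit. In 20,000 simulated null trials for each of five patterns (last visit week 24), the error was 4.6–5.4% at every visit.

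**Single follow-up.** Reading A leaves one value per participant, so the two variance components are not identifiable. Reading B has two values: the model variance is V_00 + V_11 − 2V_01, the true value, so R = 1 and the error is 5%.

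**The case against.** The strongest reply is that nothing in the documents shows the assumption to be wrong. They report no correlation between visits and no SD by visit; fading correlation is a general expectation. Under constant covariance the planned model is right. The entry thresholds (SNOT-22 of at least 25, polyp score of at least 5) could compress the baseline SD alone, and then the level is 5% (A) or 3% (B), with no inflation. This stands: a reader might infer that the late-visit intervals are too narrow as a matter of fact, and the documents do not support that.

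The size also depends on two things the SAP leaves open: the response coding and the visits modelled. Table 1 has no row for the polyp score. With weeks 16 and 20 only, change scores give about 5%. Early visits are not uniformly conservative either: at week 4, reading B gives about 6% in the fading patterns. The SAP names no primary time point, so late visits cannot be called the ones that decide the trial.

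The single-follow-up point holds only under reading A. That is the more literal reading of the SAP, but estimating changes at each visit is compatible with B. Table 1 is also an imperfect guide to which lung measures were repeated: the SAP lists microspirometry changes as outcomes, while Table 1 marks microspirometry at visit 2 only.

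A reader might further infer bias from missing visits, since a likelihood analysis under missing-at-random relies on its covariance. All calculations here used complete, balanced data, so no such harm has been shown.

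What survives is that correlation goes unchecked, no fallback is named, and the sensitivity analyses cannot detect a misfit.

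**Conclusion.** The point holds in conditional form. The planned covariance can misstate visit-specific uncertainty, and the SAP has no safeguard against that. If correlation fades, with 47 per arm and the full schedule to week 20, the last-visit test runs at about 6.5–10% on change scores or 10–17% with baseline as a repeated response, and the week-0 test at about 1–4%. With constant correlation and variance it runs at 5%, and on change scores with only weeks 16 and 20 modelled it runs at about 5%. These figures assume complete data, normal outcomes, equal covariance in both arms and time as a factor. They describe what the model allows; they are not an estimate of the error in this trial. The single-follow-up problem needs no covariance assumption but does need the change-score coding. This is a worthwhile, inexpensive improvement and does not show that the reported results are wrong.

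**What to change.** - State whether the response is the change score or the raw score with baseline as a time level, and list the visits modelled for each outcome. Reconcile the last visit (week 20 in the protocol tables; eight weeks after a 16-week period in the SAP).
- Fit visit as a category with an unstructured within-participant covariance, REML, and Kenward-Roger or Satterthwaite degrees of freedom. Fix the fallback order in advance: heterogeneous Toeplitz, then heterogeneous AR(1). At a minimum, use cluster-robust standard errors with the planned model.
- If the response is a change score, analyse outcomes with one post-baseline value (by Tables 1 and 2: spirometry, eNO, blood count) by ANCOVA of the visit-7 value on baseline and treatment.

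The cost is SAP wording and a re-run in R; no new data are needed. The downside is more covariance parameters for 94 participants: 6 × 7/2 = 21 for six change scores, or 7 × 8/2 = 28 with baseline as a response. That is why the fallback order is needed. Reporting the new fit beside the planned one would show whether the choice matters here.

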ASA challenge is conducted during the second visit if needed, according to modified international protocol (15-16). FEV1 should be at least 1.5 L and > 60% of predicted before challenge or desensitization. Patient will receive 25 mg ASA at a hospital setting. If no remarkable symptoms are seen, patient will receive 1-2 hours later another 25 mg ASA at a hospital setting.

ASA challenge positive result:

1. Naso-ocular alone: a 30 % or > increase in at least one of the following VAS (0-10 cm) scores: nasal obstruction, nasal discharge, postnasal drip, eye itching. These may exist with or without objective signs of increased nasal turbinate swelling/discharge or eye redness in examination.
2. Naso-ocular (please see 1.) and a 15% or > decline in FEV1 or in PEF (Classic reaction)
3. Lower respiratory reaction only (FEV1 or PEF declines by >20%)
4. Laryngospasm with or without 1-3 (flat or notched inspiratory curve)
5. Systemic reaction: hives, flush, gastric pain, hypotension

Patients Randomization and the treatment arms I-II occurs after 1st (or 2nd for ASA challenged) visit. The patients are randomized to two treatment arms: I) subcutaneous injections of placebo once per month for 16 weeks II) subcutaneous injections of Mepolizumab once per month for 16 weeks. Mepolizumab 100 mg / Placebo (NaCl solution)

is injected subcutaneously once per month, for a total of 16 weeks. GSK provides the randomization codes to each center.

Table1 the study protocol

| Time | -4 weeks | -2 weeks | 0 weeks | 4 weeks | 8 weeks | 12 weeks | 16 weeks | 20 weeks |
|--|---------------|----------------------|----------------|----------------|----------------|----------------|-----------------|--------------|
| Visit | 1 | 2 | 3 | 4 | 5 | 6 | 7 | 8 |
| | Rekrytointi | ASA-aslustus | 1. pistoskerta | 2. pistoskerta | 3. pistoskerta | 4. pistoskerta | Seurantakäynti | Loppukäynti |
| Name of the visit | Recruitment | ASA-challenge | 1st injection | 2nd injection | 3rd injection | 4th injection | Follow-up visit | End of Trial |
| Informed Consent | x | | | | | | | |
| Review Inclusion / Exclusion Criteria | x | x No flu 2 we before | x | | | | | |
| Medical History comorbidities | x | | | | | | | |
| Randomization | x | x | | | | | | |
| Visiting Doctor | x | x | x | x | x | x | x | x |
| Visiting Nurse | x | x | x | x | x | x | x | x |
| Review of Concomitant Medication | x | x | x | x | x | x | x | x |

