Statistics. Data analysis will be carried out on the relationship between Mepolizumab and placebo treatment. Variables tested in the statistical models include age, gender, symptoms, exacerbations, infections, medications, endoscopic findings, sick leave, allergy, side-effects of treatment, hospitalizations, and other factors at different time-points. Student's t test (or KW, MWU tests, in case of not normally distributed sample), as well as adjusted linear regression models are used for continuous measures. A statistical analysis plan (such as correction for multiple testing) will be drawn up with advice from the statistical department at the University of Helsinki.

We will use several software: R 3.0.2, SPSS 22.0 Statistical Software Package (SPSS, Chicago, IL) and STATA (Release 13.1 software, StataCorp, Texas, USA). For comparisons, the results will be analyzed by Logistic regression, Student's t-, Chi-square, (nonparametric) Fisher's exact and Mann Whitney U test. P-values less than 0.05 are considered statistically significant. Results of logistic regression are reported as odds ratios (OR) with 95% confidence intervals. All models will be adjusted by selected covariates (potential confounding factors).

Sample handling

The samples will be stored at Helsinki Biobank or at the University of Helsinki.

Table 2. Samples and their schedule. The sample protocol is reduced in KYS and TAYS.

| Time | -8 weeks | -4 weeks | 0 weeks | 4 weeks | 8 weeks | 12 weeks | 16 weeks | 20 weeks |
|--|---------------------|---------------------------|---------------------|-------------------------|---------------------|---------------------|--|---------------------|
| Visit | 1 | 2 | 3 | 4 | 5 | 6 | 7 | 8 |
| Name of the visit | Recruitment | ASA-challenge (if needed) | 1st injection | 2nd injection | 3rd injection | 4th injection | Follow-up visit | End of Trial |
| Nasal cotton/swab samples (Microbiome, RNA) | x | xx | | | | | x | |
| Nasal biopsies under local anesthesia | X2 | x | | | | | X2 | |
| Nasopharyngeal aspirate (Microbiome) | x | | x | x | x | x | x | x |
| Fasting blood sample 18 ml ¹ | x EDTA, plasma 9 ml | xx EDTA, plasma 9+9 ml | x EDTA, plasma 9 ml | EDTA DNA 4 ml, CPT 8 ml | x EDTA, plasma 9 ml | x EDTA, plasma 9 ml | x EDTA, plasma 9 ml; EDTA DNA 4 ml, CPT 8 ml | x EDTA, plasma 9 ml |
| Biobank 0-blood sample (voluntary) | X | | | | | | | |
| Blood sample (CBC, WBC differential, S-IgE allergen profile) + ECG | X | | | | | | x | |

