No imputation methods were applied for missing data. To assess the robustness of the findings and the plausibility of the missing-at-random assumption, sensitivity analyses were performed. These included a complete-case analysis restricted to participants with available data at all time points and an analysis excluding participants who received systemic oral corticosteroids

for exacerbations at any point during the trial. The corticosteroid exclusion analysis evaluated the coprimary outcomes (Nasal Polyp Score and SNOT-22 total score) as well as lung function outcomes, including relative changes in peak nasal inspiratory flow, peak expiratory flow, forced expiratory volume in one second, and corresponding microspirometry measures. Sensitivity analyses were conducted in the per-protocol population on an available-case basis using the same statistical models, confidence intervals, and significance thresholds as the primary analyses. Consistency of results across analyses was used to support the validity of the primary findings. All statistical analyses were performed using R statistical software, version 4.5.1.

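### Two coprimary endpoints are compared at every follow-up visit at p<0.05 with no primary visit, success rule or adjustment, so the primary false-positive rate is not held at 5%

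*SAP*

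**What the plan says.** The SAP analyses the coprimary endpoints and the continuous secondary outcomes as changes from baseline, using mixed models with treatment, time and their interaction. On the comparisons it says: "Group-specific changes from baseline were estimated at each follow-up time point", and "treatment effects were assessed by comparing differences in these estimated changes between groups". On the threshold: "A two-sided significance level of $p < 0.05$ was applied to all analyses", and "no formal adjustment for multiple comparisons was performed". The two endpoints are named where the corticosteroid-exclusion sensitivity analysis is described, which "evaluated the coprimary outcomes (Nasal Polyp Score and SNOT-22 total score").

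The protocol (Data management, Statistics paragraph) had left multiplicity to the SAP: "A statistical analysis plan (such as correction for multiple testing) will be drawn up". Protocol Table 1 schedules post-dose visits at weeks 4, 8, 12, 16 and 20, with SNOT-22 at every visit. It has no row labelled polyp score, but an ENT visit takes place every time.

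Neither document, as supplied, names a primary time point or says whether success needs one coprimary endpoint or both. On the last assessment, the SAP describes a 16-week treatment period "followed by an additional eight-week observation period without treatment, after which final measurements were obtained". The last two columns of Protocol Table 1 are "16 weeks | 20 weeks".

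**The concern.** A 5% threshold protects the primary claim only if it is clear in advance which comparison, or which combination, makes up that claim. Here the plan produces a treatment difference with its own p-value at each visit for each of two endpoints. It does not say which of them decides the trial. A significant SNOT-22 difference at week 8 and a significant polyp-score difference at the last visit would have equal standing under the text, although one is on treatment and the other is after the last injection. The sample size, by contrast, was built on one SNOT-22 comparison at 0.05. What is at stake is whether a reader of the results can take a p-value below 0.05 on a coprimary endpoint at face value.

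**Working it through.** **1. The plan's own figure.** Inputs from the protocol's power calculation: SNOT-22 difference 9, SD 17, two-sided 0.05, power 0.80.

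n per arm = 2(1.960 + 0.842)² × (17/9)² = 15.70 × 3.568 = 56.0. The t-test version gives 56.98, so 57, as stated. Allowing for 5% discontinuation, 57/0.95 = 60 per arm, or 120 in total, as stated.

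The difference of 13 in the same paragraph would give 28 per arm, so it is not the basis of the 57; that is a separate matter. The planned 5% therefore belongs to a single comparison.

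**2. Number of comparisons.** 2 endpoints × 5 post-dose visits = 10. Week 0 is left out because it is the visit of the first injection. The protocol's longer primary list (VAS scores and exacerbation rate as well) is not used.

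**3. Benchmark.** If the ten tests were independent, 1 − 0.95¹⁰ = 40.1%. They are not, so this figure is too high.

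**4. Correlated tests.** The method was simulation of 400,000 null draws per setting of ten normal test statistics, each significant if |z| > 1.96. The correlations are assumptions; the documents give none.
- Between visits: 0.5 to 0.8. The value 0.5 is what a shared baseline alone produces under compound symmetry: the covariance of two changes is σ²(1−ρ) and the variance of each is 2σ²(1−ρ).
- Between endpoints: 0 to 0.5.

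| Rule for a positive trial | Visit correlation 0.5 | Visit correlation 0.8 |
|---|---|---|
| Any one of the ten | 31-33% | 22-24% |
| Both endpoints, each at any visit, neither endpoint affected | 3-5% | 2-3% |
| Both endpoints at the same, freely chosen visit, neither affected | 1-4% | 1-3% |
| One endpoint truly works; the other is significant at some visit | 18% | 13% |
| One fixed visit, either endpoint, unadjusted | 9-10% | 9-10% |
| One fixed visit, both endpoints, neither affected | at most 1% | at most 1% |

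The ranges within cells come from the between-endpoint correlation. The fourth row is the error of a both-endpoints claim if the working endpoint is sure to be significant, so it is an upper figure. With four visits instead of five, the first rule gives 20-29%.

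**5. Power at the analysed size.** With 47 per arm, the noncentrality is (9/17) × √(47/2) = 2.57. The t-test then has about 72% power at 0.05 and about 61% at 0.025.

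**6. Last visit.** Protocol: the fourth injection is at week 12 and the trial ends at week 20, so 12 + 8 = 20. SAP: a 16-week treatment period and a further eight weeks, so 16 + 8 = 24.

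**The case against.** The strongest reply is that coprimary is often taken to mean that both endpoints must succeed. On that reading the error when neither endpoint responds is about 2-5%, and a reader who quoted 22-33% as this trial's false-positive rate would be assuming a rule that the SAP never states. That stands. The higher range is the consequence of one possible rule. The both-endpoints reading still leaves the visit open, however, and then gives up to 13-18% when only one endpoint truly works. Nor does the SAP say that this reading is the intended one.

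Other points have some force:
- The SAP says that changes are estimated at each visit; it does not call each visit a separate primary hypothesis. The ten comparisons also depend on the polyp score being taken at every visit, which is inferred from the ENT visits.
- The absence of an adjustment is stated openly, and results are given with 95% confidence intervals. The protocol named multiplicity only as an example of SAP content, so the SAP breaks no specific promise.
- The SAP reports blinded analysis, with the code opened after the primary analyses. This guards against steering model choices by arm. It does not reduce the number of tests or settle which visit leads the report.
- An opening part of the SAP was not in the supplied text and could contain a primary visit or a success rule.
- The final measurements might be the implied primary time point, but the text does not call them primary and their timing is unclear.

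A reader might also infer that a favourable visit was picked after the results were known. Nothing in the documents shows that.

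**Conclusion.** The concern holds in conditional form. Followed as written, the supplied plan does not hold the primary false-positive rate at 5%, because the deciding visit and the one-or-both rule are both open and no adjustment is made. The size is about 22-33% if any one of ten comparisons suffices. If both endpoints are needed but the visit is free, it is about 2-5% with no effect on either endpoint and up to 13-18% with a true effect on only one.

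These figures rest on the assumed correlations and on both endpoints being scored at five post-dose visits (explicit for SNOT-22, inferred for polyp score). The documents do not support the flat statement that the trial has a one-in-four or one-in-three chance of a false positive. Confidence is medium, given the inferred visit schedule and the part of the SAP that was not available. The mismatch over the last visit is a separate inconsistency and does not change these numbers.

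**What to change.** Name one primary visit for both coprimary endpoints. Week 16 (visit 7) is a natural example, since it closes the stated 16-week treatment period, though the documents do not single it out. Then state one of two rules:
- Success requires both endpoints at two-sided p<0.05 at that visit. No splitting of alpha is needed, and the error is at most 5% whichever endpoint is truly affected.
- If one endpoint suffices, apply Holm or Hochberg across the two. Unadjusted, this rule would run at 9-10%.

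Report the other visits and outcomes as estimates with 95% confidence intervals, without significance claims.

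The SAP is written largely in the past tense and already reports 47 per group, so it should also say when the visit and the rule were set. If that was after unblinding, label them post hoc and show both endpoints at all visits; naming a visit at that stage does not by itself restore error control.

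Separately, reconcile the last visit (week 20 in the protocol, week 24 by the SAP's wording) before describing it as an off-treatment result.

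The text change is a few sentences. The statistical cost is power. With 47 per arm, SNOT-22 alone has about 72% power for a difference of 9, so requiring both endpoints cannot exceed that. If one suffices, SNOT-22 has about 61% power when tested at 0.025, the level it faces under Holm or Hochberg if the polyp score is not significant. Other visits also lose their claim to significance.
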